In 2020 members of our team led a nationwide survey of NZ ED staff (n=1,372) to determine rates of burnout. In 22 EDs 711 (52%) nurses, 364 (27%) doctors, and 295 (22%) auxiliary staff were recruited. Overall rates of burnout, as determined by the Copenhagen Burnout Inventory (CBI),³ were very high with 59.5% reporting personal burnout, 54.7% reporting work-related burnout and 19.4% reporting patient-related burnout. Of the three worker cohorts, nurses reported the highest proportion of burnout with 68.8%, 63.0% and 25.8% for personal, work-related, and patient-related domains respectively. These findings are higher than rates seen in Australasian EM doctors, Danish human service sector staff and NZ senior medical officers (Table 5).

Table 5 Percentage of staff burnout in NZ ED staff compared with other cohorts

| CBI Burnout Domain | NZ ED staff 2020¹¹ n=1,372 % (mean, SD) | NZ SMOs 2020²⁹ n=2,102 | NZ SMOs 2015³⁰ n=1,487 | Australasian EM doctors 2019³¹ n=729 | Danish human service sector staff 2004³² n=1,917 |
|---------------------------|---|---|---|---|---|
| Personal | 59.5% (51.5, 17.7) | 49.3% | 50.1% | 45% | 22.2% |
| Work-related | 54.7% (49.9, 19.1) | 43.5% | 42.0% | 50% | 19.8% |
| Patient-related | 19.4% (31.0, 18.9) | 16.7% | 15.7% | 13% | 15.9% |

NZ=New Zealand; ED=Emergency Department; CBI=Copenhagen Burnout Inventory; SMOs=Senior Medical Officers; SD=Standard Deviation.

Post COVID-19 pandemic, the US Surgeon General has identified healthcare worker burnout as one of four priority areas in healthcare in USA.³³ In NZ, our new health system (Te Whatu Ora, Te Aka Whai Ora) identifies “develop an inclusive health workforce” as one of six priority actions.³⁴

Solutions

Problems with workplace wellbeing and burnout are complex, multi-factorial, with no easy solutions.²⁰ While there is a paucity of high-quality evidence involving our population (staff who work in emergency departments) an outline of salient literature and concepts related to interventions to improve wellbeing and reduce burnout in healthcare staff assists directing future research.

Emergency Department Setting

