| 
Primary research question:
 
• Does a multicomponent positive participatory organisational intervention package, based on individual, group and system-level components, improve burnout in NZ ED staff? 
Primary hypothesis:
 
• That a multicomponent positive participatory organisational intervention package improves workplace wellbeing, as determined by the CBI, in NZ ED staff. 
Secondary research questions:
 
• Does a multicomponent positive participatory organisational intervention package improve workplace wellbeing in NZ ED staff?• Does a multicomponent positive participatory organisational intervention package improve quality in ED systems?• Is a multicomponent positive participatory organisational intervention package feasible in a NZ ED setting? |
|---|

- Is a multicomponent positive participatory organisational intervention package acceptable to NZ ED staff?

Secondary hypotheses:

- That a multicomponent positive participatory organisational intervention package improves workplace wellbeing in NZ ED staff.
- That a multicomponent positive participatory organisational intervention package improves ED quality.
- That a multicomponent positive participatory organisational intervention package is feasible in a NZ ED setting.
- That a multicomponent positive participatory organisational intervention package is acceptable to NZ ED staff.

Methods

The Intervention

The intervention package will consist of three components targeting different levels of the HCO: the individual, the group, and the system. An initial Engagement visit to sites by the PI will involve presentations made to stakeholders and opportunities to discuss the intervention. A study start time will be established for each site in consultation with the Local Champions Group. It is anticipated that this will be within 2 months of the site Engagement visit. The intervention will take place over 12 months.

Individual-Level Component

Individual interventions must be acceptable, relevant and feasible for a given individual. An ability for participants to choose an intervention most acceptable to them is important.⁴⁷ Staff will be offered an opportunity to participate in an individual intervention. (Details and evidence for each are provided in the Individual-Level Interventions section). Participants will choose one of three possible interventions. These are:

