- Three Good Things^{15,16,96}
 - Requires daily participation by writing down and considering what is going well in a participants life, and their role in that, for 15 days.
- Mindfulness⁵⁰
 - An online guided MBI for 10 minutes per day for 10 days.
- Looking forward¹⁶
 - An optimism/hope intervention that requires consideration of hoped-for future goals and experiences. Participants are prompted to engage 7 times over 28 days to consider and write about something they are looking forward to at different future time points.

Group-Level Component

Local Champions are key to the success of the program. In consultation with their local stakeholders, and mindful of acceptability and achievability, they will decide upon an intervention targeting the group as a whole. (Details and evidence can be found in the Whānau/Group/Culture/Team-Level Interventions section). LCs will choose one from the following:

- Clinical Event Debriefing (CED)¹⁸
 - Structured debriefing for all team members following important clinical events is challenging in a busy ED environment. Addressing barriers to implementation of usable debriefing tools is required for this to become embedded in ED culture.
- Learning from Excellence⁵⁸
 - A system which can effectively and efficiently capture and feedback to staff episodes of excellent care, as determined by peers, is required.

System-Level Component

This is aimed at improving the capability for all ED staff to engage in meaningful quality improvement. The Quality Improvement Learning System (QILS) is characterised by the following features:

- consumers and frontline staff highlight issues that affect quality of care.
- triage and prioritisation of those issues.
- allocation resource for work on prioritised improvement initiatives.
- staff participation and leadership in improvement work.
- feedback to staff and consumers.
- improvement training for staff.

While each feature of QILS will be adaptable to each context and informed by our recent research, the important characteristics will be present in all cases.

Improvement Training and Coaching

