Training in Quality Improvement (QI) methods, with an emphasis on the local and ED contextual factors, will be delivered by an expert in QI training. Training will be delivered online. Individual and group coaching will be delivered by trained QI coaches. Monthly meetings of all LCG personnel will be opportunities to share lessons and build camaraderie required for sustainability. Further details of the training and coaching components are found elsewhere.

Local Champions Group

A Local Champions Group (LCG) will be critical to success at each site. The LCG will have up to 5 personnel and be a diverse composition of the local ED team, including one or more of senior doctors, nurses, other ED team members, consumers, and mana whenua. The LCG will be in the best position to understand local needs, liaise with local leaders, liaise with the investigators, and oversee many parts of the intervention in their ED. Each member of the LCG will attend the training and coaching program.

The study website

The study website provides a repository of important information for all those involved in the research. Established in 2020 and hosted by Squarespace, the website can be accessed via QR code or via the web address (www.woweated.com).

Access to open and password protected pages enables different groups access to relevant information. Participant information including about the various individual-level interventions will be available to participants, accessible via a QR code or the web address. Electronic links will allow participants to provide informed consent and access the intervention of their choice. In addition, Local Champions will have access to other information, for example group-level intervention information and links, and requirements for QI training and coaching.

The site will be maintained and modified by the PI, with advice from our University of Auckland IT specialist when required.

Study Design

A prospective multisite before and after study, using mixed methods, of the multicomponent intervention package in NZ EDs. The logistics of introducing a complex intervention into a series of EDs make compliance with randomisation, as in a randomised stepped wedge cluster study, impractical and unrealistic.

Study Setting

Individual NZ Emergency Departments will be the setting.

Site Selection

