 - patient did not wait rates, and
 - ED length of stay (LOS) over intervention year.
 - Seasonally adjusted daily staff absence, vacancies, monthly resignations, and Bradford Scale Score.
 - Compliance with the 6 targets of Te Tumu Whakarae for Māori workforce development.¹⁰²

Participants

Sample Size

Power

Differences of ≥ 5 on the CBI work-related burnout scale are considered clinically significant.¹² A sample size of 900 staff participants over 8 EDs will have 90% power to detect a change of ≥ 5 (2-tail $\alpha=0.05$).

Recruitment

Site selection is discussed above. All staff at each study site are eligible for the interventions. Participation of staff will rely upon local champions. REDCap Public Survey Links for survey distribution to participants will be used to maximise usability, anonymity and the ability to collect data. Participation by staff will be voluntary.

Māori Participation

Recruiting and retaining a Māori ED health workforce is fundamental to the advancement of Māori health and are tenets of the Ministry of Health He Korowai Oranga framework, the ACEM Te Rautaki Manaaki Mana (Māori Health Strategy),⁶ and the Māori Workforce development targets agreed to by DHBs.¹⁰² While Māori are currently under-represented in the NZ ED workforce, by maximising workplace wellbeing and reducing burnout, staff and patients benefit, particularly Māori, who most stand to benefit by health systems that are responsive to Māori needs and healthcare aspirations now and far into the future. The team has active involvement of experienced Māori emergency care leaders in clinical care, advocacy and research.

Interventions that may benefit Māori staff and patients can be undertaken by participating individuals and departments. For example, an area for improvement related to Te Ao Māori may be identified by staff, and an improvement program undertaken.

Timeframe

Implementation

Two waves of implementation will begin in March 2023 and 2024 respectively. Each wave will have between three and five EDs. Lessons learned from wave 1 will inform the implementation of interventions in wave 2. The intervention and study periods will be for 12 months.

Data collection

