Via RedCAP survey software. Staff survey at baseline (demographics: age range, gender,¹⁰³ work group, ethnicity,¹⁰⁴ years of experience at current ED) and 12 months of CBI and other measures. Routine ED data for triage compliance, did not wait rate, ED LOS, staff absence and resignations and Te Tumu Whakarae targets.

Analysis

Statistical methods

The primary and secondary outcomes will be compared pre and post intervention using a general linear mixed model with site as a random factor. Additional analyses of the primary outcome will be undertaken based on workforce group (nurse vs. other), and ethnicity (Māori vs. non-Māori), to test for differential effects of the intervention among these subgroups.

Longitudinal measurement of outcomes for individuals, that is, data-linkage and comparing results from the pre-and post-intervention surveys, is required for robust assessment of effects of the intervention. Balanced with the need for robust assessment is the need for participant confidentiality.

[figure not shown]
REDCap Public Survey Links for survey distribution to participants will be used to maximise usability, anonymity and the ability to collect data. The answers to the following two questions will be individually consistent, enabling data-linkage of coded participant data.

The screenshot shows two separate survey questions in a REDCap interface. The first question is 'What is the name of your first primary school' with a text input field. The second question is 'In which year was your mother born?' with a text input field. Both questions have a toolbar above them with icons for edit, copy, paste, and delete, and a label 'Variable: first_primary_school' and 'Variable: mother_birth_year' respectively. Below each question are buttons for 'Add Field', 'Add Matrix of Fields', and 'Import from Field Bank'.

Figure 1 Two data points for data linkage

A Public Survey Link will again be used to distribute the post-intervention survey. Respondents will be asked if they participated in the pre-intervention survey. All demographic questions will be the same as the pre-intervention survey.

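### With site as the only named random factor, the pre-post model as usually read leaves between-site variation in change out of the standard error; a random site-by-period effect with about 7 df should be specified

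*Protocol*

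**What the plan says.** Under Analysis, Statistical methods, the protocol says that primary and secondary outcomes are compared pre and post intervention "using a general linear mixed model with site as a random factor". It names no site-by-period term, participant effect or degrees-of-freedom method. The same section calls linkage of individual responses necessary for a robust assessment.

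The design is described under Study Design as "A prospective multisite before and after study, using mixed methods, of the multicomponent intervention package in NZ EDs". Every site receives the package and there is no control.

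Other sections show that the package will differ between EDs:
- Group-Level Component: local champions choose one of two group interventions.
- System-Level Component: "While each feature of QILS will be adaptable to each context and informed by our recent research", only the core characteristics are common to all sites.
- Timeframe, Implementation: "Lessons learned from wave 1 will inform the implementation of interventions in wave 2".

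The primary research question in Table 8 is whether the package can "improve burnout in NZ ED staff". Under Sample Size, Power: "A sample size of 900 staff participants over 8 EDs will have 90% power to detect a change of ≥ 5", two-sided at 0.05.

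**The concern.** The intervention is introduced to a whole ED at once, and its content and delivery vary by ED. Staffing, leadership and demand over 12 months will also move whole departments up or down, even if the package has no effect. The true change is therefore likely to differ between sites.

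A site random intercept describes how EDs differ in level. Each ED contributes to both surveys, so that level drops out of the pre-post difference, exactly when a site has equal numbers before and after and nearly so otherwise. The intercept therefore does nothing for variation in change. The standard error falls with the number of staff responses, although only 8 departments changed. For a question about NZ ED staff in general, the confidence interval can then be too narrow and the type I error can exceed 5%.

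**Working it through.** **Inputs**
- SD of the CBI work-related score: 19.1 (Protocol, Table 5, 2020 survey). The sample-size text does not say that this value was used.
- 8 sites and 900 staff (Sample Size). Read here as 900 per survey; fewer are considered below.
- Pre-post correlation r = 0.5 where responses are linked: assumption.
- tau, the between-site SD of true 12-month change: assumption, shown from 0 to 4 points.

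**The plan's own figure.** The stated 90% power can be neither reproduced nor refuted, because its SD, correlation and clustering assumptions are not given. With SD 19.1 and no clustering, two unlinked surveys of 900 give more than 99.9% power for 5 points, and 307 per survey would give 90%. Reaching 90% with 900 per survey takes a design effect of about 2.93 (ICC about 0.017 at 112.5 per site) or an SD of about 32.7.

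**Sampling variance of the mean change, without tau**
- Unlinked: 2 × 19.1² / 900 = 0.811, SE 0.900.
- Linked: 2 × 19.1² × (1 − 0.5) / 900 = 0.405, SE 0.637.

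**True SE** = sqrt(sampling variance + tau²/8)

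| tau | 0 | 1 | 2 | 3 | 4 |
|---|---|---|---|---|---|
| Unlinked | 0.900 | 0.967 | 1.145 | 1.391 | 1.677 |
| Linked | 0.637 | 0.728 | 0.951 | 1.237 | 1.551 |

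**SE that the model reports** on the random-intercept reading: 0.900 for unlinked data; 0.900 for linked data with site only, since the pairing is ignored; 0.637 for linked data with a participant effect.

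**Type I error** = 2 × (1 − Phi(1.96 × reported SE / true SE))

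| tau | 0 | 1 | 2 | 3 | 4 |
|---|---|---|---|---|---|
| Linked, site only | 0.6% | 1.5% | 6% | 15% | 26% |
| Unlinked | 5% | 7% | 12% | 20% | 29% |
| Linked, with participant effect | 5% | 9% | 19% | 31% | 42% |

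Example, unlinked at tau 3: 1.96 × 0.900 / 1.391 = 1.27, which gives 20%. Simulation agrees: unlinked 12.2% and 20.4% at tau 2 and 3; linked with site only 6.1% and 15.4%.

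**Break-even for linked data with site only.** Ignoring the pairing overstates the variance by 0.811 − 0.405 = 0.405. This offsets tau²/8 up to tau = sqrt(8 × 0.405) = 1.8. Below that value the test is conservative.

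**Fewer respondents.** With 450 per survey, unlinked, the error is 9% at tau 2 and 13% at tau 3.

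**Site-level alternative.** A t-test of the 8 site mean changes on 7 df kept type I error at 4.8% to 5.3% in simulation. Its power for 5 points with 900 per survey, from the noncentral t with noncentrality 5 / true SE:

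| tau | 2 | 3 | 4 |
|---|---|---|---|
| Unlinked | 96% | 87% | 73% |
| Linked | 99% | 93% | 79% |

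**The case against.** The strongest objection is that the protocol does not say intercept only. The primary outcome is a mean change and linkage is planned, so the model may be meant for linked individual change scores. In that case the site term does not cancel: it is itself the between-site variance in change. In simulation (8 sites of 112 pairs, SD 19.1, r = 0.5, tau 0 to 4) that model has a type I error of about 4% to 9% with a normal test and about 3% to 5% with Satterthwaite-type df. This stands, and it means that the wording is inadequate rather than proven wrong. Against it, the section speaks of outcomes compared pre and post, and open survey links will bring in people who answer only one survey and have no change score.

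Random-effects detail is also often left to a statistical analysis plan, which is not at hand. Here, however, the protocol itself names the random structure.

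A reader might infer that the false-positive rate is 15% to 40%. The documents do not support that as a flat statement. No tau is given, the upper end needs a participant effect that the protocol does not name, and the site-only model on linked data is conservative below a tau of about 1.8.

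A reader might also infer that this model is why the result cannot extend beyond the 8 EDs. Site Selection says that the first EDs select themselves and are well placed to change, and the study has no control. Both limit generalisation whatever model is fitted. For the average change in these 8 EDs alone, leaving out tau²/8 would not be an error; the concern rests on the wider target in Table 8.

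**Conclusion.** The point holds in a conditional form. On the usual random-intercept reading, the named model omits tau²/8 from the variance of the pre-post contrast, while the protocol's own design makes site-specific change likely.

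The size depends on an undocumented tau, on linkage and on the number of respondents. With SD 19.1, 900 per survey and r = 0.5 where linked, the excess over 5% is small or absent at tau 1 or less. It is material from about tau 2 for unlinked data or linked data with a participant effect, and from about tau 3 for linked data with site only. Adding a participant effect alone, a natural step once responses are linked, raises the error at any tau above 0, so the two terms should be settled together. One sentence that allows both a model close to 5% and a model at 31% (tau 3) is too loose for a primary analysis.

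**What to change.** In Statistical methods, specify:
1. a fixed effect of period, a random site effect and a random site-by-period effect, with a participant random effect where responses are linked;
2. Kenward-Roger or Satterthwaite degrees of freedom, about 7 for the period effect;
3. a t-test of the 8 site mean changes on 7 df as a check, and as the reported interval if the site-by-period variance is estimated as zero.

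If the model is meant for linked individual changes, say so, give the same df method, and say how people who answer only one survey are handled.

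Restate the power under Sample Size with the assumed SD, pre-post correlation and tau, and say whether 900 means respondents per survey, linked pairs or a total.

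The cost is analysis and sample-size wording, with no change to conduct. The interval will be wider, and the stated power may fall below 90%, as it does in the site-level test at tau 4 (73% to 79%). Site self-selection and the absence of a control remain and should be stated as separate limits on the conclusion.

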We propose a multicomponent intervention that addresses individuals' needs, is adaptable to local context, and that targets three organisation levels: the individual, the group/whānau, and the system. We hypothesise this intervention will reduce burnout and contribute toward the three areas NZ ED staff previously identified as beneficial to wellbeing, that is, a supportive team culture, provide professional development opportunities, and improve the provision of high-quality care.¹² This is described in detail in Methods.

Research Aims, Objectives, Hypothesis

The aim is to investigate if a multicomponent positive participatory organisational intervention aimed at improving the delivery of high-quality care, that is insider-led, includes the voice of frontline staff and accounts for complexity, will improve NZ ED staff burnout as determined by pre- and post-intervention assessment using the Copenhagen Burnout Inventory (CBI).

Hypothesis

Implementation of a multicomponent positive participatory organisational intervention will improve ED staff workplace wellbeing and burnout.

Table 7 Research Objectives

| |
|---|
| 
The Objectives of this research are to:
 
• Refine and use a multicomponent positive participatory organisational intervention package, based on individual, group and system-level components, in participating NZ EDs.• Undertake a before and after study of the multicomponent intervention package in NZ EDs, including:
○ A quantitative assessment of the intervention package on staff burnout, wellbeing, and ED quality measures.○ A mixed methods process evaluation of the intervention package examining fidelity and staff acceptability. |
|---|

Research Questions

Table 8 Research Questions

| |
|---|

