The screenshot shows a survey question in a REDCap interface: 'Did you answer the QILS4WoWe@NZEDs survey in March 2023?'. A dropdown menu is open over the question, showing three options: 'Yes' (selected with a checkmark), 'No', and 'Unsure'. The question has a toolbar above it with icons for edit, copy, paste, and delete, and a label 'Variable: answered_survey_before'. Below the question are buttons for 'Add Field', 'Add Matrix of Fields', and 'Import from Field Bank'.

Figure 2 Post-intervention survey question about prior participation

The answers to the two questions that generate data points for data linkage questions (Figure 1) will be asked and can be matched and used to aggregate data from the pre- and post-intervention survey for analysis.

In the rare instance when data from these questions are not precise enough to discriminate between respondents, in addition, other demographic data will be used for data linkage. These will be questions about gender and profession.

Process Evaluation.

As well as understanding the direction and magnitude of effects of the proposed interventions, an understanding of what hindered and facilitated these effects, and how and why these effects occurred is important for a full understanding of the research.¹⁰⁵ We propose a process evaluation.

Data collected for the process evaluation will be quantitative, and include the following:

- Quantitative data relevant to the workings of the LCG will be collected in an excel sheet:
 - log of activities
 - training and coaching sessions provided
 - proportion of LCG attendance at each session
 - number of meetings
- Individual-level component of the intervention:
 - number of hits on website containing individual level intervention
- Group-level component of the intervention:
 - number of debriefs recorded; or
 - number of responses recorded
- System-level component of the intervention:
 - summary of:
 - problems identified,
 - solutions enacted,
 - effect of solutions.

Results will be anonymised by hospital.

Ethics and dissemination

Safety

All ED staff have access to Employee Assistance Programs. In addition, participants will be informed of and encouraged to seek help from other local sources, such as colleagues and participant's GP. Some departments also have a departmental psychologist who all staff can access.

Consent

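### The acceptability hypothesis has no direct or defined measure: the objectives promise a mixed-methods process evaluation, but the Methods confine it to quantitative items

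*Protocol*

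**What the plan says.** Three places in the protocol set the commitment:

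- Table 7 (Research Objectives) lists as an objective: "A mixed methods process evaluation of the intervention package examining fidelity and staff acceptability".
- Table 8 (Research Questions) asks: "Is a multicomponent positive participatory organisational intervention package acceptable to NZ ED staff". It pairs this with a secondary hypothesis: "That a multicomponent positive participatory organisational intervention package is acceptable to NZ ED staff".
- Study Design describes "A prospective multisite before and after study, using mixed methods, of the multicomponent intervention package in NZ EDs".

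The Process Evaluation section opens with an explanatory aim, that "an understanding of what hindered and facilitated these effects, and how and why these effects occurred is important". It then fixes the kind of data: "Data collected for the process evaluation will be quantitative, and include the following". The list that follows contains:

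- for the Local Champions Group, an activity log, the training and coaching sessions provided, the proportion attending, and the number of meetings;
- for the individual level, "number of hits on website containing individual level intervention";
- for the group level, "number of debriefs recorded; or" a count of recorded responses;
- for the system level, a summary of problems, solutions and the effect of solutions.

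**The concern.** The objectives and the data-collection section disagree about what will be gathered. A mixed-methods evaluation needs a qualitative strand, and a hypothesis about acceptability needs something that records whether staff found the package acceptable. The Process Evaluation section provides neither. Because the gap lies in which data are collected, a statistical analysis plan could not close it afterwards.

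The protocol itself gives acceptability weight. Its background notes that ED staff may not accept a sole focus on individual-level interventions. The Methods require individual interventions to be acceptable, relevant and feasible. The Dissemination policy foresees possible national roll-out if the intervention succeeds, and that decision would draw on acceptability. There is a second, smaller problem at the individual level: the one process measure listed there does not show how many staff took up the component, or which option they took.

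**Working it through.** No figure in the protocol needs to be reproduced. The check is whether anything in the planned data can answer the acceptability hypothesis.

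**Step 1. Where acceptability could be measured.**

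| Place in the protocol | What is planned | Direct acceptability measure | Qualitative data from staff |
|---|---|---|---|
| Outcome, ED Staff | CBI domains, UWES-9, psychological empowerment, WHO-5 | none | none |
| Outcome, Department | QILS issues and solutions, departmental and workforce data, Māori workforce targets | none | none |
| Assessment methods and Data collection (survey content) | demographics, burnout, wellbeing, engagement, empowerment | none described | none described |
| Process Evaluation | the list given above | none | none; the data are stated to be quantitative |

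**Step 2. Qualitative work elsewhere.** The protocol reports survey comments, interviews and a focus group from 2022. These assessed departments' baseline capability before the package was used, so they cannot show whether staff found it acceptable.

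**Step 3. Secondary hypotheses against data.** There are four: workplace wellbeing, ED quality, feasibility and acceptability. Staff scales address the first and departmental data the second. Delivery and activity records bear on the third. For the fourth there is no direct measure, and no rule that turns any listed item into one. That is one of four.

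**Step 4. What website hits can show.** Each participant chooses one of three options: a 15-day daily exercise, a 10-day mindfulness course, or one with 7 prompts over 28 days. The protocol does not say whether a hit is a page load or a unique visitor. Suppose, purely as an assumption, that every session loads the page once and that 900 hits are recorded. That total would fit:

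- 900 / 15 = 60 people completing the first option;
- 900 / 10 = 90 completing the second;
- 900 / 7 ≈ 129 completing the third;
- or 900 people who looked once and went no further.

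The total is invented. The illustration shows only that, if hits are page loads, one count fits very different numbers of users. If hits were unique visitors, persons could be approximated, but option and completion would still be unknown.

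**Step 5. Another possible source.** The section on the study website says electronic links will let participants consent and reach their chosen intervention, and the Consent section requires electronic consent before participation. These records might yield starters per option. They appear neither among the outcomes nor in the process list, and they would not show completion or acceptability.

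**The case against.** The strongest reply is that the plan is less bare than it looks. Participation is voluntary, so staff-raised QILS issues, recorded debriefs or positive-feedback responses, and champions' attendance all carry some behavioural information about acceptability. The process list goes beyond activity counts: it has an attendance proportion and a summary of the effect of solutions. It is introduced as a list of what the data include, so it is formally open. The survey instrument is not reproduced in full, so an acceptability item might exist. The protocol also says this study is part of a larger mixed-methods project, which may explain the label.

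Much of this stands as a limit on the point, but it does not remove it. Behavioural counts are proxies, and the protocol neither names them as acceptability measures nor sets a criterion. The list may be open, but its opening sentence still confines it to quantitative data. An item that might exist in an unseen questionnaire is not a planned measure, and Table 7 makes acceptability an objective of this study.

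A reader might infer three stronger things, and the documents support none of them:

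- **That individual uptake cannot be determined at all.** Consent and access links could supply starter counts. The gap is that they are not specified as data.
- **That a null primary result could not be told apart from low uptake of the package.** Group- and system-level activity is recorded. Only the individual component, one of three, has weak exposure data, and the protocol gives no uptake figure from which to calculate any dilution.
- **That the primary result is undermined.** The primary outcome is the change across all ED staff, and its analysis does not depend on knowing who used what.

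**Conclusion.** The point holds as an internal contradiction with a practical consequence. Table 7, Table 8 and Study Design promise a mixed-methods evaluation and an answer on acceptability, while the Process Evaluation section limits the data to quantitative items that do not measure it directly. Followed as written, the study would have no direct or defined measure for one of its four secondary hypotheses and no qualitative strand during or after the intervention. For the individual component it would have one listed measure, which does not count persons, option chosen or completion.

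This rests on the outcome list, the survey content as described and the process list. It would fall away in part if the full questionnaire already contains acceptability or uptake items, in which case the protocol should say so. The primary outcome and its analysis are not affected. It should still be corrected, because the remedy is cheap and missing data of this kind cannot be recovered once the 12-month survey has closed.

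**What to change.** 1. Add a short fixed set of items at the end of the 12-month survey, after the existing scales so that the pre/post measures are undisturbed: an acceptability rating for each of the three levels; which individual intervention was started and whether it was completed; whether the group component and QILS were used; and one free-text item to supply the qualitative strand.
2. List counts of electronic consent or access per individual option as uptake data in the Process Evaluation section. Keep website hits as a descriptive item only, and state what a hit is.
3. Amend the sentence on data type in the Process Evaluation section so that it agrees with Table 7 and Study Design.
4. Treat any summary of CBI change by self-reported use as descriptive only. Users choose themselves, so it cannot establish that exposure caused the change. Acceptability ratings will likewise come only from staff still in post who answer at 12 months, and the report should say so.

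If the added items are not wanted, the consistent alternative is to remove the mixed-methods label and the acceptability objective, question and hypothesis.

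The cost is a slightly longer survey and some extra burden. The protocol's own background notes survey fatigue, which is a reason to keep the set short. The rest is wording.
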